### **11.1 Types**

Any adverse and unintentional sign (abnormal and clinically significant analytical result) associated or not to the use of the drugs will be considered an adverse event.

### **11.2 Clinical signs secondary to the use of the study drug**

- i. Vaginal itching sensation
- ii. Water discharge during treatment
- iii. Vaginal erythema
- iv. “Sandy” sensation during sexual intercourse
- v. Acute systemic toxicity due to boric acid
- vi. Chronic toxicity due to the use of boric acid
- vii. Bacteraemia caused by *Lactobacillus spp.*

### **11.3 Serious Adverse Events**

Information on Serious Adverse Events (SAE) and Unexpected Serious Adverse Reactions (USAR) with **suspicion of causal relationship** with the treatments under study will be collected and recorded in the Serious Adverse Events notification form (RD223/2004). These serious adverse events must also be notified to the Spanish Agency of Medicines and Medical Products (AEMPS). The AEMPS will be notified by the ESIC, for which reason the investigator must notify them within 24 hours of knowing. Only serious, unexpected AEs related to treatments under study will be reported to the AEMPS.

Any adverse event or adverse reaction is considered to be a SAE or USAR when, at any dose, it:

- Leads to the death of the patient,
- Threatens the life of the subject,
- Forces the subject to be hospitalized or to extend their stay,
- Leads to permanent or significant disability, or
- Results in a congenital anomaly or malformation.

The intensity of the AE will be classified as mild, moderate or severe. The investigator will record the relationship of the study product with the AE according to the following causality terms:

- Related: The AE follows a reasonable time sequence from the moment of exposure to the product. It cannot be explained by the subject's clinical condition or by the study procedures/conditions. The AE decreases after the discontinuation of the study product and reappears once the study product is re-administered.
- Potentially related: The AE follows a reasonable time sequence from the time of exposure to the product, but may have been caused by the subject's clinical condition or by the study procedures/conditions.
- Unlikely related: The temporary association between the AE and the study product is such that it is unlikely that there is any reasonable relationship between them. The relationship is not likely due to other possible explanations.
- Not related: The AE has undoubtedly been caused by the subject's clinical condition or by the procedures/conditions of the CT. A reasonable explanation must be given, for example, that the product has not been consumed under research or an incompatible temporary relationship.
- Not assessable: The report indicating an adverse reaction cannot be judged because the information available is insufficient or contradictory, and no extra data can be added or verified.

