### 6.3.3 Baseline Visit – $V_0$ (inclusion)

After the case history and initial examination, which will serve to substantiate the suspicion of VV due to infection, patients will be recommended to participate in the trial provided they meet the inclusion/exclusion criteria. Once the patient Information Sheet (PIS) has been handed over, the patient has signed the Informed Consent (IC) form and the investigator has verified that the patient meets the inclusion and exclusion criteria, they will proceed to fill in the CRF baseline visit sections.

During this first visit, socio-demographic data, relevant clinical history and gynaecological history will be recorded. The investigator will assess the patient's symptoms by recording the presence of clinical signs and symptoms of infectious VV (stinging, itching, erythema, oedema, abnormal vaginal discharge, etc.) and the *Sobel score* (see section 7.0). The vaginal pH determination test will then be carried out and the samples for the different laboratory tests will be collected, which will consist of: spreading the vaginal discharge sample on a slide to subsequently count the *Lactobacillus spp.* and collecting the discharge sample with a swab that will also be used for the diagnostic confirmation culture and for the fresh vaginal smear. The samples will be stored properly according to the instructions specified in the manual of use of the sampling kit until the samples are collected.

The patient will be given the treatment corresponding to the code assigned to her, reminding her that she has the possibility of changing treatment group, at the time that she deems appropriate. If the assigned treatment is ineffective or

is not tolerable, the patient may contact the hospital to bring the first control visit forward and request a change of treatment.

During the baseline visit, the patient will be given a CRF which she must fill in and return at the end of the visit and a card with a link to the online home CRF (Patient diary) that must be filled in over the course of the study. The home CRF will be used to monitor the patient during the follow-up weeks. The home CRF may also be delivered on paper and the patient must deliver it later.

The investigator will give the patient product for one treatment cycle (which may range from 3 days (Clindamycin) to 7 days (boric acid 150 mg, *L. gasseri*, *L. rhamnosus*)).

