## **11 ADVERSE EVENTS**

The Adverse Events (AE) that appear during the study will be assessed. An AE is any harmful event in a patient after randomisation and during a study, even if it is considered not related to the treatment of the study. ***In this CT, AEs will be collected and recorded in the CRF, provided that they are serious (if they cause clinical signs or symptoms and are considered clinically significant) and/or are related to the treatments under study.***

Diseases or medical conditions that were present before starting the medication under study will only be considered AEs if there is a worsening after the start of the study treatment (any procedure specified in the protocol).

As far as possible, AEs will be described according to:

- Duration (start and end dates).
- Degree of severity (mild, moderate, severe).
- Relationship with medication under study (suspected/not suspected).

- Action(s) taken to correct it.

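### The *Related* causality term is all but unreachable in a one-course trial, and the causality level that admits an adverse event to the CRF is not defined

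*Combined protocol and SAP*

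**What the plan says.** **Two causality scales.** Section 11 lists the attributes by which an AE is described, among them "Relationship with medication under study (suspected/not suspected", which gives two levels. Section 11.3 then states: "The investigator will record the relationship of the study product with the AE according to the following causality terms". It lists five terms: *Related*, *Potentially related*, *Unlikely related*, *Not related* and *Not assessable*. Although this sits in the section on serious events, it is worded for any AE. No rule links the five terms to the two.

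**Definition of Related.** Section 11.3 asks for a reasonable time sequence and then adds two further conditions with no qualifier for cases where they do not apply: "It cannot be explained by the subject's clinical condition or by the study procedures/conditions" and "The AE decreases after the discontinuation of the study product and reappears once the study product is re-administered". *Potentially related* asks for the same time sequence, "but may have been caused by the subject's clinical condition or by the study procedures/conditions".

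**Recording rule.** Section 11 defines an AE whether or not it is related to treatment, but then restricts what is entered: "AEs will be collected and recorded in the CRF, provided that they are serious" (glossed in brackets as symptomatic and clinically significant) "and/or are related to the treatments under study".

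**Exposure.** Under section 6.3.3 the patient receives "product for one treatment cycle". Section 10.1 allots one box per study-group patient at baseline. Under section 6.2.3, hypersensitivity or lack of effectiveness moves the patient to the other treatment.

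**The concern.** A causality scale is useful only if its terms can be reached and if every event has a term that fits. Here the highest term depends on an observation that the design does not plan to make.

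That would be a labelling matter if all AEs were recorded. They are not: relatedness is one of the two conditions for entering the CRF. A five-level rating can be collapsed to two levels at analysis, but an event that was never entered cannot be recovered.

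Safety and tolerance is a secondary objective (sections 1.10 and 3.2), AEs are among the main assessment variables (section 7.1), and the AE rate is an end point (section 7.3). The trial is open (sections 1.11 and 10.2) and multicentre, and no central causality review is described. An undefined threshold can therefore be applied differently by centre and by arm.

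**Working it through.** No arithmetic reproduces this point, because the documents give no AE rate, error level, power or sample-size derivation. The check sets the definitions side by side and traces an event through them.

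**Step 1. Can *Related* be reached?** It needs plausible timing, no other explanation, improvement on stopping, and reappearance on re-administration. Planned exposure is daily dosing for 7, 6 or 3 days (sections 1.16 and 6.4), supplied once. The mixed-infection rescue sequence for the study group (section 6.2.3) goes to clotrimazole and then clindamycin, and does not return to the study product. Patients in whom rescue also fails are discontinued (section 6.2.4). No planned step stops a product and gives the same one again. Only an unplanned pause and resumption within a course could supply the missing observation.

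**Step 2. Does every product-caused event have a term?** Assume no re-exposure:

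| Event | *Related* | *Potentially related* |
|---|---|---|
| Another cause is possible | Fails (other explanation; no re-exposure) | Fits |
| No other cause is possible | Fails (no re-exposure) | Fails (presumes another possible cause) |

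The clearest product reaction is the one that fits neither term. The expected local reactions in section 11.2 (itching, watery discharge, erythema) overlap with the disease signs recorded in section 6.3.3, and itching and erythema are also Sobel items (section 7.1). They will usually fall under *Potentially related*, and the plan does not say whether that level counts as related.

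**Step 3. Does the event enter the CRF?** There are two routes.

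- *Serious, as glossed in section 11.* A symptomatic and clinically significant AE enters whatever its causality. This sense differs from the list in section 11.3 (death, threat to life, hospitalisation, disability, congenital anomaly).
- *Related.* An AE that does not meet that gloss depends on this route alone. For a product-caused event without re-exposure:

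| Meaning given to related in section 11 | Admitted by this route |
|---|---|
| (a) Only the term *Related* | None (0%) |
| (b) *Related* or *Potentially related* | Those with a possible alternative cause; those with none have no fitting term |
| (c) Suspected, on the two-level scale | All that the investigator suspects |

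Capture by this route therefore runs from 0% to all suspected events.

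**Step 4. Sensitivity of the end point.** Section 6.8 gives a minimum of 50 patients at 1:1, so 50 / 2 = 25 per arm. If the AE rate is expressed as the proportion of patients with an event (an assumption, since section 7.3 does not say), each patient whose only event goes unrecorded moves an arm's rate by 1 / 25 = 4 percentage points. This shows sensitivity and does not estimate how many events would be lost.

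**Step 5. Related inconsistencies.** In section 11.3, serious events are collected on suspicion of causality, but authority reporting is limited to related ones, and neither word is tied to a level. The five-term scale speaks of the study product, while the recording rule covers all treatments under study, so its use in the control arm is not stated.

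**The case against.** The strongest defence is that section 11 never says its ordinary word related means the top term of section 11.3. The surrounding text points the other way. The scale in section 11 itself is suspected or not suspected, serious events are collected on suspicion, and four of the five terms would serve little purpose for events admitted on causality if only *Related* ones were recorded. This stands. It makes reading (c) plausible, but it does not make it the stated rule.

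Second, the broad gloss on serious lets in symptomatic, clinically significant events regardless of causality, including the expected local reactions when they are judged significant. This also stands. What remains exposed is the milder event judged not clinically significant.

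Third, daily dosing leaves room for a paused and resumed course, so the re-administration condition is not strictly impossible. This stands too, and *rarely if ever met* is as far as the text goes.

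Fourth, the CRF is not among the documents and its code list might settle the threshold. Selective collection is also an explicit choice in a postmarketing pilot, and AEs are analysed descriptively only (section 8.2). These points limit the consequence. They do not supply the missing term for an event with no alternative cause, or a threshold in the protocol.

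**Conclusion.** The defect holds as one of definition and collection. Two causality scales differ and are not mapped. *Related* will rarely if ever be met under the planned exposure. A product-caused event with no other explanation and no re-exposure fits neither *Related* nor *Potentially related*. Events outside the section 11 gloss on serious are recorded or lost on an unblinded judgement whose threshold is tied to no level.

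Three stronger conclusions are tempting, and the documents do not support them:

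- A reader might infer that the recording rule under-counts related events, or that the AE rate is close to zero by construction. That needs reading (a), which no section states, and it ignores the route through serious. With no AE rates given, the size of any under-count is unknown.
- A reader might infer that the two scales contradict each other. Five terms can be collapsed to two once a rule is stated.
- A reader might infer that the tolerability end points are distorted. Section 7.3 lists them separately from the AE rate, and nothing derives them from AE causality.

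The descriptive AE rate is affected, and possibly authority reporting. The efficacy comparison is not. The conclusion assumes that the CRF contains no definition that settles the threshold.

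**What to change.** - Use one causality scale in sections 11 and 11.3, or state how the five terms map to suspected and not suspected.
- Remove re-administration as a necessary condition of *Related*, and keep it as supportive evidence where it happens to occur. This concerns the wording of the scale only and calls for no change in how patients are treated.
- Record every AE in both arms with its seriousness and causality level, and apply the relatedness filter at analysis. State that the scale applies to the control products as well.
- State in advance which levels count as suspected or related for analysis and for authority reporting, including how *Not assessable* is handled.
- Reconcile the two meanings of serious in sections 11 and 11.3.

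The cost is protocol wording, a revised CRF code list and a few more AE lines per patient. The change is needed before data collection, because events left out of the CRF cannot be restored afterwards.

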#### **11.4 Action taken and resolution of AE**

The investigator will record the action(s) taken with the product and the effects of the event for each of the AEs, according to the following:

- Action taken in relation to the product
- Resolution

### **11.5 Follow-up of patients with AE**

Patients can be withdrawn from the CT at any time. Patients who have been withdrawn from the study due to an AE must be monitored by the investigator until the clinical result of the AE is determined.

